15.7.2. Handling of Missing Data

Element	Reporting Detail			
General	Missing data occurs when any requested data is not provided, leading to blank fields on the collection instrument:			
	 These data will be indicated using a "blank" in subject listing displays. Unless all data for a specific visit are missing in which case the data is excluded from the table. 			
	 Answers such as "Not applicable" and "Not evaluable" are not considered to be missing data and should be displayed as such. 			
Outliers	• Any participants excluded from the summaries and/or statistical analyses will be documented along with the reason for exclusion in the clinical study report.			
PK	Adjustments to the derivation of PK parameters where NQ values are present in the data will be performed according to how extensive the NQ values are and which treatment groups the NQ's are present in. Refer to the Standards for the Handling of NQ impacted PK Parameters documentation.			
PET	Missing PET measurements will not be imputed.			

15.7.2.1. Handling of Missing and Partial Dates

Element	Reporting Detail
General	Partial dates will be displayed as captured in subject listing displays.
Adverse Events	 The eCRF allows for the possibility of partial dates (i.e., only month and year) to be recorded for AE start and end dates; that is, the day of the month may be missing. In such a case, the following conventions will be applied for calculating the time to onset and the duration of the event: Missing Start Day: First of the month will be used unless this

Element	Reporting Detail
	is before the start date of study treatment; in this case the study treatment start date will be used and hence the event is considered On-treatment as per Appendix 4: Study Phases and Treatment Emergent Adverse Events. o Missing Stop Day: Last day of the month will be used, unless this is after the stop date of study treatment; in this case the study treatment stop date will be used. Completely missing start or end dates will remain missing, with no imputation applied. Consequently, time to onset and duration of such events will be missing.
Concomitant Medications/ Medical History	 Partial dates for any concomitant medications recorded in the CRF will be imputed using the following convention: If the partial date is a start date, a '01' will be used for the day and 'Jan' will be used for the month If the partial date is a stop date, a '28/29/30/31' will be used for the day (dependent on the month and year) and 'Dec' will be used for the month. The recorded partial date will be displayed in listings.

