5.2. Baseline Definitions

For all endpoints (except as noted in baseline definitions) the baseline value will be the latest pre-dose assessment with a non-missing value, including those from unscheduled visits. If time is not collected, Day 1 assessments are assumed to be taken prior to first dose and used as baseline.

Parameter	Study Assessment Period			
	1		2	
Baseline Used in Data Display	Dosing Period 1 Day -1 or Day 1 (Pre- Dose)	Dosing Period 2 Day -1 or Day 1 (Pre- dose)	Dosing Period 2, Baseline scan (≤2 Weeks Pre-Dose)	
Pharmacodynamics				
Volume of Distribution (V_T) , not corrected for air volume			X	
Volume of Distribution (V _T), corrected for air volume			X	
Standardised Uptake Values (SUV), not corrected for air volume			X	
Standardised Uptake Values (SUV), corrected for air volume			X	

Parameter	Study	Study Assessment Period			
	1		2		
Baseline Used in Data Display	Dosing Period 1 Day -1 or Day 1 (Pre- Dose)	Dosing Period 2 Day -1 or Day 1 (Pre- dose)	Dosing Period 2, Baseline scan (≤2 Weeks Pre-Dose)		
Safety					
12 Lead ECG	X	X			
Vital Signs	X	X			
Laboratory Assessments	X	X			
FEV ₁ and FVC (absolute & % predicted)	X	X			
DLCO (absolute & % predicted)	X				

For all pharmacodynamics and safety displays, baseline will be labelled 'Pre-dose'.

If Pre-dose % predicted FVC in Period 2 is missing Pre-dose % predicted FVC in Period 1 will be used as baseline value instead for PET data analysis.

If Day -1 and Day 1 pre-dose values are missing, screening value for Period 1 will be used as baseline. Unless otherwise stated, if baseline data is missing no derivation will be performed and baseline will be set to missing.

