15.4. Appendix 4: Study Phases and Treatment Emergent Adverse Events

15.4.1. Study Phases

Assessments and events will be classified according to the time of occurrence relative to study treatment.

Study Phase	Definition
Pre-Treatment	Date ≤ Study Treatment Start Date
On-Treatment	Study Treatment Start Date < Date ≤ Study Treatment Stop Date + 1
Post- Treatment	Date > Study Treatment Stop Date + 1

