15.4.2. Treatment Emergent Flag for Adverse Events

Flag	Definition
Treatment Emergent	 If AE onset date is on or after treatment start date & on or before treatment stop date. Study Treatment Start Date ≤ AE Start Date ≤ Study Treatment Stop Date +1 For studies with greater than one treatment period (e.g., Period 1 and Period 2), if AE onset is during one period and worsens during a later period it would be counted in both periods. For the initial period the logic would be as above. For the later period the logic would use the treatment dates associated with the later period: Treatment Period Start Date ≤ AE Worsening Date ≤ Study Treatment Stop Date + 1

NOTES:

- If the study treatment stop date is missing, then the AE will be considered to be On-Treatment.
- Time of study treatment dosing and start/stop time of AEs should be considered, if collected.

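### The SAP's cap on a missing adverse event stop day puts the stop before a recorded onset that falls after the treatment stop date, and the phase table contradicts the adverse event rules on the treatment start date

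*SAP*

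**What the plan says.** SAP 15.7.2.1 allows AE dates to be recorded as month and year only, and sets conventions "for calculating the time to onset and the duration of the event". For a missing stop day: "Last day of the month will be used, unless this is after the stop date of study treatment"; if it is after, the treatment stop date is used. For a missing start day, the first of the month is used unless it precedes treatment, in which case "the study treatment start date will be used and hence the event is considered On-treatment as per Appendix 4".

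SAP 15.4.1 opens: "Assessments and events will be classified according to the time of occurrence relative to study treatment". Its table defines Pre-Treatment as "Date ≤ Study Treatment Start Date". On-Treatment begins strictly after the start date and ends one day after the stop date.

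SAP 15.4.2 defines a treatment-emergent AE in words as one with onset "on or after treatment start date & on or before treatment stop date", and then by the formula "Study Treatment Start Date ≤ AE Start Date ≤ Study Treatment Stop Date +1".

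SAP 2.3 gives one nebulised dose in each of two dosing periods. Protocol 9.2.1 collects AEs from the first dose to the follow-up visit, which the Protocol Synopsis places 7–14 days after the final dose. SAP 15.4.3 has a separate category for AEs from 72 hours after the second dose to the end of follow-up.

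**The concern.** A cap at the treatment stop date might suit a trial with continuous dosing and AEs confined to the treatment period. Here treatment is a single dose, so the stop date is a dosing day, and the plan expects AEs in the days after it. For those AEs the cap pulls the imputed stop back past onset.

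The phase labels raise a second, separate problem. A programmer who follows the reference from 15.7.2.1 to Appendix 4, and applies the phase table there, labels an AE on the treatment start date Pre-Treatment. Section 15.7.2.1 says the reference should give On-treatment.

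At stake are the derived duration of follow-up AEs with partial stop dates and the phase label of AEs on the first dosing day. Safety is a primary objective, so both should be derived correctly even if few events are involved.

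**Working it through.** **1. The stop-day rule in general.** Let T be the treatment stop date, O the recorded onset date, E the last day of the recorded stop month and S the imputed stop. The rule in 15.7.2.1 is S = E if E ≤ T, otherwise S = T.

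An AE cannot end before it starts, so E ≥ O. If O > T, then E > T, the cap applies, and S = T < O. This holds for every AE with a recorded onset day after T and a missing stop day. Duration counted as S − O + 1 equals T − O + 1, which is zero or negative. For onsets 1 to 14 days after T it runs from 0 down to −13 days.

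**2. Examples, last dose 15 March.**
- Onset 18 March, stop recorded as March: E = 31 March, so S = 15 March, 3 days before onset.
- Onset 27 March, stop recorded as April: E = 30 April, so S = 15 March, 12 days before onset and outside the recorded month.

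**3. Enumeration.** With a final dose on each day of 2018 (an assumed year that does not affect the logic), onset 1–14 days later and the stop in the onset month, there are 365 × 14 = 5,110 cases. All 5,110 give a stop before onset. This confirms the inequality; it is not an estimate of frequency.

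**4. Which stop date.** The SAP does not say whether the stop date is per period or overall. Post-final-dose AEs fail on both readings. For AEs starting between the doses, with doses 7–28 days apart:
- Cases: 365 × Σ(g − 1) for g = 7 to 28 = 365 × 363 = 132,495.
- Per-period reading (T = first dose): all 132,495 fail, by step 1.
- Last-dose reading (T = second dose): none fails, because T and E are both on or after O.

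**5. Start day also missing.** The start then moves to the first of the onset month, or to the treatment start date if that is later. If the onset month is the month of T, the imputed start is on or before T and the duration is not negative. It is negative only when onset falls in the next month. In the step 3 cases that is 12 × (1 + 2 + … + 14) = 12 × 105 = 1,260 of 5,110. In the rest the imputed stop still precedes the true onset, but the derived duration does not show it.

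**6. The phase boundary.** Take treatment start 1 March and stop 15 March, dates spanning both periods:

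| Date | 15.4.1 phase | 15.4.2 formula |
|---|---|---|
| 28 February | Pre-Treatment | not emergent |
| 1 March | Pre-Treatment | emergent |
| 2–16 March | On-Treatment | emergent |
| 17 March | Post-Treatment | not emergent |

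The two rules differ only on the treatment start date. If start and stop are taken per period, each dosing day is a start date and both are Pre-Treatment. Within 15.4.2, the words stop at 15 March and the formula at 16 March.

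**The case against.** The strongest reply is that no reported result is shown to be affected. AE Tables 2.1 and 2.2 are laid out by the dosing-period windows of SAP 15.4.3, listings show partial dates as captured, and no display title in Appendix 12 names duration, time to onset or phase. The display shells are not in the document, so use of duration in a standard listing can be neither shown nor excluded. This stands, and it limits the point to a faulty derivation rule.

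The less-than-or-equal sign in 15.4.1 may also be meant to protect baselines: SAP 5.2 says "If time is not collected, Day 1 assessments are assumed to be taken prior to first dose and used as baseline". That may explain the boundary for assessments, but the table covers events as well, and 15.7.2.1 relies on Appendix 4 for AEs. The note in 15.4.2 about using clock times, if collected, qualifies the treatment-emergent flag and leaves the phase table as it is.

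Three stronger readings are tempting, and the documents do not support them:
- A reader might infer that every AE after treatment gets a negative duration. Complete dates are untouched, completely missing dates stay missing, and with the start day also missing only some durations are negative.
- A reader might infer that both dosing days are misclassified. That is firm only for the study treatment start date; the second dosing day depends on the unstated reading.
- By date, the nine planned post-dose assessments on Period 1 Day 1 (four ECGs, four sets of vital signs, one spirometry) fall in Pre-Treatment, so a reader might infer that the safety summaries are wrong. SAP 15.5.2 uses planned time relative to dosing for summaries and derivations, and the safety tables run by dosing period, visit or planned timepoint. No affected output is identified.

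**Conclusion.** The stop-day rule is wrong as written. For an AE with a recorded onset day after the treatment stop date and a missing stop day, it always gives a stop before onset. The plan expects AEs in that interval. Washout AEs are affected as well on the per-period reading, and not on the last-dose reading.

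The phase table in 15.4.1 is inconsistent with 15.4.2 and 15.7.2.1 for AEs on the study treatment start date. The mismatch between words and formula in 15.4.2 is a matter of wording.

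The severity is minor. The fault reaches derived AE duration and phase labels only, and the PET analysis is not involved. The documents do not say how often stop days are missing. With 7 planned participants in Cohort 1 and no Cohort 2, few AEs are likely to be affected. The conclusion rests on reading the rules literally and on an AE not ending before it begins.

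**What to change.** **15.7.2.1, minimum:** add that an imputed stop date is never before AE onset. This alone removes every impossible duration.

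**15.7.2.1, preferred:** also replace the treatment-stop cap with the last day of the recorded stop month, because the date of a single dose says nothing about when an AE ended. The step 2 examples then stop on 31 March and 30 April. The drawback is longer imputed durations for AEs that the present rule does not break. An AE starting on 15 March, the last dosing day, with stop recorded as March, goes from 1 day to 31 − 15 + 1 = 17 days. Neither value is supported by data, so the choice should be stated.

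**15.4.1:** for AEs, align the boundary with 15.4.2, so that an AE on the treatment start date, from the dose onward or untimed, is On-Treatment. Leave the rule for untimed Day 1 assessments in 5.2 unchanged.

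**Wording only:** make the text of 15.4.2 match its formula (stop date + 1), and state whether treatment start and stop dates are per period or overall. The windows in 15.4.3 stay as they are.

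The cost is an edit to one imputation rule, one table and a sentence or two, with small programming changes before the final database freeze. No new data are needed.

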15.7.2.2. Handling of Missing Data for Statistical Analysis

For statistical analysis purposes, data will be assumed to be Missing at Random (MAR) and no imputation will be conducted.

15.8. Appendix 8: Values of Potential Clinical Importance

15.8.1. Laboratory Values

Haematology					
Laboratory Parameter	Units	Categor	Clinical Concern Range		
		y	Low Flag (< x)	High Flag (>x)	
		Male		0.54	
Haematocrit	Ratio of 1	Female		0.54	
Tracmatoerit	Ratio of 1	Δ from BL	↓0.075		
		Male		180	
Haemoglobin	g/L	Female		180	
Tracmogroom		Δ from BL	↓25		
Lymphocytes	x10 ⁹ / L		0.8		
Neutrophil Count	x10 ⁹ / L		1.5		
Platelet Count	x10 ⁹ / L		100	550	
While Blood Cell Count (WBC)	x10 ⁹ / L		3	20	

Clinical Chemistry					
Laboratory Parameter	Units	Category	Clinical Concern Range		
			Low Flag (< x)	High Flag (>x)	
Albumin	g/L		30		
Calcium	mmol/L		2	2.75	
Creatinine	umol/L	Δ from BL		↑ 44.2	
Glucose	mmol/L		3	9	
Magnesium	mmol/L		0.5	1.23	
Phosphorus	mmol/L		0.8	1.6	
Potassium	mmol/L		3	5.5	
Sodium	mmol/L		130	150	
Total CO2	mmol/L		18	32	

Liver Function				
Test Analyte	Units	Category	Clinical Concern Range	
ALT/SGPT	U/L	High	2x ULN	
AST/SGOT	U/L	High	2x ULN	
AlkPhos	U/L	High	2x ULN	
T Bilirubin	μmol/L	High	1.5xULN	
T. Bilirubin + ALT	μmol/L	High	1.5xULN T. Bilirubin +	

Liver Function			
Test Analyte	Units	Category	Clinical Concern Range
	U/L		2x ULN ALT

15.8.2. ECG

ECG Parameter	Units	Clinical Concern Range			
		Lower	Upper		
Absolute	Absolute				
Absolute QTc Interval	msec		>450		
Absolute PR Interval	msec	< 110	> 220		
Absolute QRS Interval	msec	< 75	> 110		
Change from Baseline					
Increase from Baseline QTc	msec		>60		

15.8.3. Vital Signs

Vital Sign Parameter	Units	Clinical Concern Range		
(Absolute)		Lower	Upper	
Systolic Blood Pressure	mmHg	< 85	> 160	
Diastolic Blood Pressure	mmHg	< 45	> 100	
Heart Rate	bpm	< 40	> 110	

Vital Sign Parameter	Units		Clinical Con	cern Range	
(Change from Baseline)		Deci	rease	Incr	ease
		Lower	Upper	Lower	Upper
Systolic Blood Pressure	mmHg		≥ 40		≥ 40
Diastolic Blood Pressure	mmHg		≥ 20		≥ 20
Heart Rate	bpm		≥ 30		≥ 20

15.9. Appendix 11: Abbreviations & Trade Marks

15.9.1. Abbreviations

Abbreviation	Description
ADaM	Analysis Data Model
AE	Adverse Event
AIC	Akaike's Information Criteria
A&R	Analysis and Reporting
ALT	Alanine aminotransferase (SGPT)
AST	Aspartate aminotransferase (SGOT)
AUC	Area under the plasma drug concentration versus
	time curve
AUC _(0-t)	Area under the plasma concentration-time curve
	from zero (0) hours to time (t)
AUC (0-inf)	Area under the plasma concentration-time curve
	from zero (0) hours (to infinity (inf)
BMI	Body mass index
BQL	Below the quantification limit
CDISC	Clinical Data Interchange Standards Consortium
C _{max}	Maximum observed plasma drug concentration
CI	Confidence Interval
CPMS	Clinical Pharmacology Modelling & Simulation
CPSR	Clinical Pharmacology Study Report
CPSSO	Clinical Pharmacology Science and Study
	Operations
CS	Clinical Statistics
CSR	Clinical Study Report
CTR	Clinical Trial Register
CV_b/CV_w	Coefficient of Variation (Between) / Coefficient
	of Variation (Within)
DBF	Database Freeze
DBR	Database Release
D	Dose
DM	Data Management
DLCO	Diffusing Capacity of the Lungs for Carbon
	Monoxide
DOB	Date of Birth
DP	Decimal Places
eCRF	Electronic Case Report Form
ECG	Electrocardiogram
EMA	European Medicines Agency
FDA	Food and Drug Administration
FDAAA	Food and Drug Administration Clinical Results
	Disclosure Requirements
FEV_1	Forced Expiratory Volume in 1 second

Abbreviation	Description		
FVC	Forced Vital Capacity		
GCSP	Global Clinical Safety & Pharmacovigilance		
GSK	GlaxoSmithKline		
μg	Microgram		
HPD	Highest Posterior Density		
HR	Heart rate		
HRCT	High Resolution Computerised Tomography		
IA	Interim Analysis		
ICH	International Conference on Harmonization		
IDMC	Independent Data Monitoring Committee		
IDSL	Integrated Data Standards Library		
IMMS	International Modules Management System		
IP	Investigational Product		
IPF	Idiopathic Pulmonary Fibrosis		
ITT	Intent-To-Treat		
λz	Terminal phase rate constant		
	_		
LLQ LSLV	Lower limit of quantification Last Subject Last Visit		
	5		
MCMC	Markov Chain Monte Carlo		
MMRM	Mixed Model Repeated Measures		
MCSE	Monte Carlo Standard Errors		
msec	Milliseconds		
mcg	Microgram		
microRNA	Micro Ribonucleic acid		
mRNA	Messenger Ribonucleic acid		
NONMEM	Nonlinear Mixed Effects Modelling		
NQ	Non-quantifiable concentration measured as		
DOY	below LLQ		
PCI	Potential Clinical Importance		
PCPS	Projects Clinical Platforms and Sciences		
PD	Pharmacodynamic		
PDMP	Protocol Deviation Management Plan		
PET	Positron Emission Tomography		
PK	Pharmacokinetic		
PKPD	Pharmacokinetic Pharmacodynamic		
PP	Per Protocol		
PopPK	Population PK		
QC	Quality Control		
QTcF	Fridericia's QT Interval Corrected for Heart Rate		
QTcB	Bazett's QT Interval Corrected for Heart Rate		
RandAll NG	RandAll New Generation		
RAP	Reporting & Analysis Plan		
RAMOS	Randomisation & Medication Ordering System		
SAC	Statistical Analysis Complete		
SAE	Serious Adverse Event		
	•		

Abbreviation	Description
SAS	Statistical Analysis Software
SI	System Independent
SD	Standard deviation
SDSP	Study Data Standardization Plan
SDTM	Study Data Tabulation Model
SDTM IG	Standard Data Tabulation Model Implementation
	Guide
SOA	Schedule of Activities
SOP	Standard Operation Procedure
SUV	Standardised Uptake Values
T	Infusion duration
TA	Therapeutic Area
TAU	Therapeutic Area Unit
TFL	Tables, Figures & Listings
t OR tlast	Time of last observed quantifiable concentration
t½	Terminal phase half-life
τ	Dosing interval
tlag	Lag time before observation of drug
	concentrations in sampled matrix
T_{max}	Time of occurrence of C _{max}
ULQ	Upper limit of quantification
ULN	Upper limit of normal
UK	United Kingdom
VC	Variance-Covariance
VS	Vital Signs
V_{T}	Volume of distribution
WBC	While Blood Cell Count

15.9.2. Trademarks

Trademarks GlaxoSmithKline Companies	of Group	the of
HARP		

Trademarks not owned by the GlaxoSmithKline Group of Companies
NONMEM
SAS
WinNonlin

15.10. Appendix 12: List of Data Displays

15.10.1. Data Display Numbering

All data displays will combine Dosing Period 1 and Dosing Period 2 unless this has been explicitly described otherwise or the actual data display requires Dosing Period 1 and Dosing Period 2 as separate rows. For the interim analyses subject randomisation numbers were scrambled when individual data was shown while for the final analyses after breaking study blind actual randomisation numbers will be shown

The following numbering will be applied for RAP generated displays:

Section	Tables	Figures	
Study Population	1.1 to 1.16	N/A	
Safety	2.1 to 2.12	2.1 to 2.4	
Pharmacodynamic	3.1 to 3.8	3.1 to 3.8	
Pharmacokinetic	4.1 to 4.3	4.1 to 4.4	
Section	List	ings	
ICH Listings	1 to 29		
Other Listings	30 t	o 41	

15.10.2. Mock Example Shell Referencing

Non IDSL specifications will be referenced as indicated and if required example mock-up displays provided in Appendix 13: Example Mock Shells for Data Displays.

Section	Figure	Table	Listing
Study Population	POP_Fn	POP_Tn	POP_Ln
Safety	SAFE_Fn	SAFE_Tn	SAFE_Ln
Pharmacodynamic	PD_Fn	PD_Tn	PD_Ln
Pharmacokinetic	PK_Fn	PK_Tn	PK_Ln

NOTES:

• Non-Standard displays are indicated in the 'IDSL / Example Shell' or 'Programming Notes' column as '[Non-Standard] + Reference.'

15.10.3. Deliverables

Delivery [Priority] [1]	Description
IA SAC	Interim Analysis Statistical Analysis Complete
SAC	Final Statistical Analysis Complete

NOTES:

1. Indicates priority (i.e. order) in which displays will be generated for the reporting effort

15.10.4. Study Population Tables

Study	Study Population Tables					
No.	Population	IDSL / Example Shell	Title	Programming Notes	Deliverable [Priority]	
Subje	ct Disposition					
1.1.	ITT	ES1	Summary of Participant Disposition for the Participant Conclusion Record	ICH E3, FDAAA, EudraCT	SAC	
1.2.	ITT	SD1	Summary of Treatment Status and Reasons for Discontinuation of Study Treatment	ICH E3	SAC	
1.3.	ITT	ES4	Summary of Participant Disposition at Each Study Epoch	ICH E3	SAC	
1.4.	All Participants	ES6	Summary of Screening Status and Reasons for Screen Failure	Journal Requirements	SAC	
1.5.	Enrolled	NS1	Summary of Number of Participants by Country and Site ID	EudraCT/Clinical Operations	SAC	
Protoc	col Deviation					
1.6.	All Participants	DV1	Summary of Important Protocol Deviations	ICH E3	SAC	
Popul	Population Analysed					
1.7.	All Participants	SP1	Summary of Study Populations	IDSL	SAC	

Study	Study Population Tables					
No.	Population	IDSL / Example Shell	Title	Programming Notes	Deliverable [Priority]	
1.8.	All Participants	SP2	Summary of Exclusions from the Per Protocol Population	IDSL	SAC	
Demo	graphic and B	aseline Char	acteristics			
1.9.	PP	DM1	Summary of Demographic Characteristics	ICH E3, FDAAA, EudraCT	SAC	
1.10.	PP	DM11	Summary of Age Ranges	EudraCT	SAC	
1.11.	PP	DM5	Summary of Race and Racial Combinations	ICH E3, FDA, FDAAA, EudraCT	SAC	
1.12.	ITT	DM1	Summary of Demographic Characteristics	ICH E3, FDAAA, EudraCT	SAC	
1.13.	Enrolled	DM11	Summary of Age Ranges	EudraCT	SAC	
1.14.	Enrolled	DM5	Summary of Race and Racial Combinations	ICH E3, FDA, FDAAA, EudraCT	SAC	
Prior	and Concomit	ant Medicati	ons			
1.15.	ITT	MH1	Summary of Current/Past Medical Conditions	ICH E3	SAC	
1.16.	ITT	CM1	Summary of Concomitant Medications	ICH E3	SAC	

15.10.5. Safety Tables

Safety: Ta	ables				
No.	Population	IDSL / Example Shell	Title	Programming Notes	Deliverable [Priority]
Adverse F	Events (AEs)				
2.1.	ITT	AE1	Summary of All Adverse Events by System Organ Class and Preferred Term	ICH E3, Overall and by Dosing period (Dosing Period 1, Dosing Period 1 follow up, Dosing Period 2 and Dosing Period 2 follow up)	SAC
2.2.	ITT	AE1	Summary All Drug-Related Adverse Events by System Organ Class and Preferred Term	ICH E3, Overall and by Dosing period (Dosing Period 1, Dosing Period 1 follow up, Dosing Period 2 and Dosing Period 2 follow up) As 2.1 notes	SAC
Laborator	ry: Chemistry	,		1	ı

Safety: Ta	Safety: Tables					
No.	Population	IDSL / Example Shell	Title	Programming Notes	Deliverable [Priority]	
2.3.	ITT	LB1	Summary of Chemistry Changes from Baseline	ICH E3, By treatment and by Dosing period (Period 1, Period 2) Includes Baseline values. Includes pre-specified parameters repeated in conventional units.	SAC	
Laborator	y: Hematolog	gy				
2.4.	ITT	LB1	Summary of Hematology Changes from Baseline	ICH E3, By treatment and by Dosing period (Period 1, Period 2) Includes baseline values.	SAC	
Laborator	y: Urinalysis					
2.5.	ITT	UR3b	Summary of Urinalysis Dipstick Results by Planned Timepoint	ICH E3, By treatment and by Dosing period (Period 1, Period 2) Includes Baseline values.	SAC	
ECG						

Safety: Ta	Safety: Tables					
No.	Population	IDSL / Example Shell	Title	Programming Notes	Deliverable [Priority]	
2.6. ITT			IDSL, By treatment and by Dosing period (Period 1, Period 2)			
	ITT	ITT EG1	Summary of ECG Findings	As above for Chemistry, using ECG findings categories (and change from baseline categories, if applicable).	SAC	
2.7.	ITT	EG2	Summary of Change from Baseline in ECG Values by Visit	IDSL, By treatment and by Dosing period (Period 1, Period 2) Includes Baseline values.	SAC	

Safety: Ta	bles				
No.	Population	IDSL / Example Shell	Title	Programming Notes	Deliverable [Priority]
Vital Sign	s				
2.8.	ITT	VS1	Summary of Change from Baseline in Vital Signs	ICH E3, By treatment and by Dosing period (Period 1, Period 2) Includes Baseline values.	SAC
Lung Fun	ction Tests: (1	FEV1, % Predicted	FEV ₁ , FVC and % Predicted FVC)		
2.9.	ITT	PFT1	Summary of Pulmonary Function Test Data	Absolute and % Predicted, by Visit	SAC
2.10.	ITT	PFT3	Summary of Change from Baseline Pulmonary Function Test Data	Absolute and % Predicted, by Visit	SAC
Diffusing	capacity of th	e lungs for carbon	monoxide (DLCO) and % Predicted DLCO		
2.11.	ITT	PFT1	Summary of Diffusing Capacity of the Lungs for Carbon Monoxide (DLCO).	Absolute and % Predicted, by Visit	SAC
2.12.	ITT	PFT3	Summary of Change from Baseline Diffusing Capacity of the Lungs for Carbon Monoxide (DLCO).	Absolute and % Predicted,	SAC

